14.3 Patient Disposition and Characteristics

Demography and other baseline characteristics will be summarized descriptively for the FAS, PP, and Safety population (if different), overall and by treatment group. For quantitative data, means, medians, standard deviations and extremes will be determined. For qualitative data, absolute and relative frequencies will be calculated. Important baseline characteristics will be further summarized by sex, race, and age.

	Trial Substance:	Ruconest®	Study No.: C1 6201 PROTECT-COVID-19-US
	Short Title:	Ruconest®: Prevention of severe SARS-CoV-2 infection in hospitalized patients with COVID-19	Sponsor: Pharming Technologies B. V.

14.4 Treatments (study drug, rescue medication, other concomitant therapies, compliance)

RhC1-INH syringes for all administration time points on a given day will be prepared by the pharmacist. The study drug including the exact time for administration of the first and subsequent syringes will be entered into the electronic prescribing system/chart or added to the paper chart. As this study involves IV administration of the IMP by nurses, patient compliance measures are not necessary. IMP will be administered by a nurse according to the site's standard procedures. Two nurses will check the IMP with respect to dose, study number and patient's identity before administration to the patient. Nurses will document the syringe number and the time of administration in the electronic or paper chart.

Use of concomitant therapies will be listed.

14.5 Efficacy

Continuous variables will be summarized using the mean, standard deviation, median, minimum, maximum values. Categorical variables will be summarized using the cell frequencies and percentage of patients in each category.

All statistical tests performed will be two-tailed with significance determined by reference to the 5 % significance level, unless otherwise stated. The null hypothesis at all times will be the equality of the treatments being compared.

Furthermore, the results will be presented graphically.

14.5.1 Primary efficacy variable

The primary endpoint WHO Ordinal Scale measure at day 7 will be analyzed by means of the nonparametric Wilcoxon rank test stratified by its baseline values with two-sided α -level of 5%. Two adaptive interim analyses after 40 and 80 patients are planned according to the Pocock adjusted levels $\alpha_p = 0.0221$. The results of the sequential groups are combined by the inverse-normal-method (Lehmacher, Wassmer, 1999). There are no prespecified futility margins, but the DSMB can stop the study in the case of insufficient interim results.

Furthermore, 95% confidence intervals will be determined, and the results will be presented graphically by means of box-and-whisker plots.

The analyses will be carried out by the trial biostatistician.

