6.2.1 Randomization

Participants will be randomized to two parallel groups in a 2:1 ratio to receive either rhC1INH (intervention) in addition to standard of care (SOC) or SOC treatment (control). Randomization will be stratified by the study site before inclusion using randomly permuted block sizes of four.

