- A negative pregnancy test before study entry/randomization. We expect the rate of female patients of childbearing age who may become pregnant to be <10% of all patients potentially eligible for this study. Due to the short treatment period (4 days) and half-life of rhC1INH (2.5 hours) an effective means of contraception is not mandatory during the hospitalization treatment phase. At least one method of contraception (oral contraceptives, barrier methods, approved contraceptive implant or abstinence) is required for the entire follow up study period
- Concomitant Interventions (treatments)

All participants will receive standard supportive care established at the sites which may include off-label use of certain drugs that are deemed to be effective in COVID-19 (e.g. hydroxychloroquine, lopinavir/ritonavir, prophylactic anticoagulation). In addition, escalation of treatment with off-label use of certain drugs (e.g. tocilizumab) in deteriorating participants is allowed during the trial. Randomization will be stratified by site to compensate for different standards of supportive care. Off-label use of drugs for the treatment of COVID-19 will be recorded in the CRF. Escalation of treatment is one outcome of interest.

Patients are allowed to use all their regular medication during the trial. In addition, patients will receive all drugs required for the treatment of COVID-19 or its consequences. The care of the participant will remain unaffected by inclusion into the study or by study group assignment.

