11.4.2 Primary Analysis

The primary endpoint WHO Ordinal Scale measure at day 7 will be analyzed by means of the nonparametric Wilcoxon rank test stratified by its baseline values with two-sided α -level of 5%. Two adaptive interim analyses after 32 and 80 patients are planned according to the Pocock adjusted levels $\alpha_p = 0.0221$. The results of the sequential groups are combined by the inverse-normal-method (Lehmacher, Wassmer, 1999). There are no prespecified futility margins, but the DSMB can stop the study in the case of insufficient interim results.

Furthermore, 95% confidence intervals will be determined, and the results will be presented graphically by means of box-and-whisker plots.

The analyses will be carried out by the trial biostatistician.

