6 SAMPLE SIZE

This is a pilot study investigating the efficacy and safety of rhC1-INH in the prevention of clinical deterioration in a high-risk population with COVID-19. There is no reliable information available on the clinical evolution of the population included in the trial. Therefore, a precise quantitative pre-definition of the sample size of a population needed to obtain clinically significant primary endpoint is not possible at this point in time.

The assumptions which are proposed and the criteria to monitor and assess the primary endpoint are as follows:

The primary endpoint is a 7-point scale and the standard deviation σ can be expected as 1.5 points. A relevant effect δ is an advantage of at least 1 point. Then, the standardized difference is about $\delta/\sigma = 0.67$. For a fixed sample size design with a two-sided significance level of $\alpha = 0.05$ and a power of $1 - \beta = 0.80$, a sample size of $N = 2 \times 38$ is necessary. Because of a nonparametric test, we add 4 patients in each group, and because of drop-outs we add also 4 patients in each group to $N = 2 \times 46$. For a 2:1-randomization, a nonparametric analysis by the stratified Wilcoxon rank-test, and an adaptive group sequential analysis, the overall sample size is estimated as $120 = 80 + 40$.

All patients are hospitalized, and it is very unlikely that the primary endpoint at Day 7 will not be measured. Nevertheless, a drop-out rate of about 10% is included.

Adaptive design:

Two interim analyses after 40 and 80 patients are planned according to the Pocock adjusted levels $\alpha_p = 0.0221$. Based on the results of an interim analysis the sample size can be adjusted (Lehmacher, Wassmer, 1999). There are no prespecified futility margins, but the DSMB can recommend stopping the study in the case of insufficient interim results.

The primary efficacy endpoint and the main secondary efficacy endpoints will be analyzed at latest at 14 days after start of treatment.

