14.2 Datasets to be analyzed, Analysis populations

A review of the database will be conducted in a blinded manner shortly before the database will be locked, and any decisions made at that meeting (blinded Data Review Meeting) concerning the statistical analysis, *e.g.*, additional outcomes and populations, pooling of sites for efficacy analysis, will be documented in the Statistical Analysis Plan (SAP).

Missing data for the primary endpoint will be imputed by means of the Last-observation-carried-forward (LOCF) method, as sensitivity analyses some alternative imputation methods like imputation of the mean and multiple imputation will be additionally performed.

The following analysis populations will be used for analysis of study data:

Safety population: The Safety Population is defined as all patients who received at least one dose of rhC1-INH. Statistical analyses will be based on the actual treatment the patient received.

Full Analysis Set (FAS)/Intention to treat (ITT) population: The FAS/ITT Population is defined as all patients who are randomly allocated to a study arm. Statistical analyses will be based on the treatment arm to which the patient was allocated. For quantitative data, the number of patients with non-missing information, means, medians, standard deviations and extremes will be determined. For qualitative data, absolute and relative frequencies will be calculated. Moreover, changes from baseline (V2, d0) will be calculated.

Per protocol (PP) population: The PP Population is defined as all patients in the FAS/ITT Population who complete the study and who do not have any major protocol violations, including the following:

- Patients who had major inclusion/exclusion criteria violations.

Sufficient compliance is expected because of IV administration of the IMP.

The PP Population will be determined by a blinded review in the Data Review Meeting (DRM) of the data prior to database lock. The primary efficacy analysis will be based on the FAS/ITT Population in this superiority trial; an additional efficacy analysis will be performed on the PP Population. The Safety Population will be used for all safety analyses.

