14.7 Multi-site study

Individual site results will be presented by means of descriptive statistical methods for the demographical and primary efficacy data.

	Trial Substance:	Ruconest®	Study No.: C1 6201 PROTECT-COVID-19-US
	Short Title:	Ruconest®: Prevention of severe SARS-CoV-2 infection in hospitalized patients with COVID-19	Sponsor: Pharming Technologies B. V.

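### Randomisation is stratified by site, but the primary Wilcoxon test is stratified by baseline score only: valid, but conservative and less efficient than a site-adjusted rank test if sites differ

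*SAP*

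**What the plan says.** Protocol 6.2.1 states: "Randomization will be stratified by the study site before inclusion using randomly permuted block sizes of four". Protocol 8.6 gives the reason: "Randomization will be stratified by site to compensate for different standards of supportive care".

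The primary test does not use that factor. Protocol 11.4.2 specifies a "nonparametric Wilcoxon rank test stratified by its baseline values", and SAP 14.5.1 repeats it: the Day 7 score is to be "analyzed by means of the nonparametric Wilcoxon rank test stratified by its baseline values". The protocol synopsis and section 9.1.1 also name only the baseline value.

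Site appears in two other places in the analysis plan. SAP 14.7 says: "Individual site results will be presented by means of descriptive statistical methods for the demographical and primary efficacy data". Protocol 11.4.1 and SAP 14.2 list "pooling of sites for efficacy analysis" among decisions that may be taken at the blinded data review shortly before database lock, with no method attached.

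The trial has 120 patients, allocated 2:1. About five to ten sites are planned in Protocol 6.1, and four to ten in Protocol 1.5.

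**The concern.** By stratifying on site for this reason, the sponsor treats site as likely to affect outcome. Balancing the arms within sites reduces the true sampling variability of the treatment comparison. A test that ignores site still counts between-site variation as noise. Its standard error is then too large, its error rate falls below nominal, and part of the efficiency gained by stratifying is lost.

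What is at stake is a few points of power in a small trial with three looks, recoverable without extra patients or data.

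**Working it through.** **The plan's own figure.** SAP 6 gives a difference of 1 point, SD 1.5, two-sided alpha 0.05 and power 0.80.
- Normal formula: 2 x (1.96 + 0.8416)² x 1.5² / 1² = 35.3, so 36 per arm. The t-test gives 36.3. Dividing by the Wilcoxon efficiency of 0.955 gives 38.0, against the stated 38.
- Total: 92 x 9/8 for 2:1 allocation = 103.5. Multiplying by about 1.17 for three Pocock looks gives about 121, against the stated 120.
- Three equal looks at 0.0221 simulate to an overall alpha of 0.0498.

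The sample size is therefore reproduced.

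**Missing input.** The between-site variance is not given, so it is assumed. A site SD of s on the log-odds scale corresponds to an intraclass correlation ICC = s² / (s² + π²/3):
- s = 0.5: 0.25 / 3.54 = 0.07
- s = 1.0: 1 / 4.29 = 0.23

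**Normal approximation, single look, total variance fixed.** With site-balanced allocation, a statistic that ignores site has variance 1 - ICC under the null. Two-sided size is 2[1 - Φ(1.96/√(1 - ICC))]. For an 80% design (noncentrality 2.8016), power is Φ((2.8016 - 1.96)/√(1 - ICC)) ignoring site and Φ(2.8016/√(1 - ICC) - 1.96) adjusting for it.

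| ICC | Size, site ignored | Power, ignored | Power, adjusted |
|---|---|---|---|
| 0 | 0.050 | 0.800 | 0.800 |
| 0.05 | 0.044 | 0.806 | 0.820 |
| 0.10 | 0.039 | 0.812 | 0.840 |
| 0.20 | 0.028 | 0.827 | 0.879 |

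**Three-look simulation, proportional odds, log OR 1.0.** Each stage is tested separately and combined by the inverse-normal method. The comparator is rank ANCOVA with additive baseline and site terms, pooling sites with fewer than 6 patients in a stage. Entries are power in %, planned / adjusted.

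| Set | Sites | SD 0 | SD 0.5 | SD 1.0 | Planned one-sided error at SD 1.0 |
|---|---|---|---|---|---|
| A (level 0.0214) | 5 | 69/69 | 66/69 | 56/64 | 1.3-1.4% |
| A | 10 | 67/67 | 61/63 | 51/56 | as above |
| B (level 0.0221, unequal sites) | 5 | 71/71 | 68/70 | 58/65 | 1.7-1.8% |
| B | 10 | 70/71 | 65/66 | 58/63 | as above |
| C (level 0.0221, ranges) | 5 | 67-69/65-67 | 60-64/60-65 | 51-55/58-63 | 1.4-1.8% |
| C | 10 | 66-67/65-66 | as above | 51-53/54-57 | as above |

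The level 0.0214 is the equal-level boundary for looks at 32, 80 and 120 (the protocol's timing); 0.0221 is the documents' value. The conclusion is the same at either. The adjusted test held its error near 2.5% (1.8 to 2.9% across settings). At SD 1.0 the matched pairs differ by 7 to 8 points with 5 sites and by 5 points with 10. Set C is reported only as ranges, and a power estimate from 1,200 runs has a standard error of about 1.4 points. The gain is therefore put at about 5 to 8 points with 5 sites and 3 to 5 with 10.

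**Second model.** This uses a latent normal score with total residual SD 1.5, a shift of 0.8, three looks at 0.0221, blocks of three and no pooling of sites. Power is planned / adjusted.
- 5 sites: 62.3 / 65.0% at ICC 0.10; 63.6 / 71.2% at ICC 0.20.
- 10 sites: 61.3 / 58.6% at ICC 0; 62.6 / 60.3% at 0.05; 63.0 / 62.9% at 0.10; 62.7 / 67.1% at 0.20.

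Blocks of four cannot give an exact 2:1 split. Mixed 3:1 and 2:2 blocks gave the same direction for error (single-look size 0.045 and 0.037 at ICC 0.10 and 0.20). With 10 sites and no pooling they gave a larger cost of adjustment when sites do not differ (59.8 / 55.3%).

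**Crossing site with baseline.** In the second model with 10 sites, a Wilcoxon test stratified by baseline x site had about 38 to 46% power, against 61 to 63% for the planned test. Many strata hold only one arm.

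**The case against.** The strongest case on the other side is that nothing promised by the plan fails. This largely stands.

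- **Validity.** A reader might infer that omitting a stratification factor invalidates the test or inflates type I error. It does the opposite: error stays at or below nominal.
- **Planned power.** A reader might take the fall from 69% to 56% as the trial losing its power. Much of that fall arises because those scenarios add site variance on top of the full residual variance, and the adjusted test falls too, to 64%. The stated SD of 1.5 is not labelled within-site. With total variance held fixed, planned-test power stays roughly flat, at about 63 to 69% across simulations. Log OR 1.0 is also smaller than the design effect: 0.67 x 1.81 = 1.21. At 1.21 with total variance fixed, the planned test gave 83 to 85%.
- **Remedy.** Adjustment is not free in every form. With 10 sites and separate site terms in each 40-patient stage, it cost power when sites differed little. Pooling every site with fewer than 6 patients avoids that, but can remove the site term altogether: 10 sites recruiting evenly average 4 patients each in a stage of 40. In such a simulation all patients were pooled at every stage, and power at SD 1.0 was 55% against 56%.
- **Already handled.** Stratified randomisation does secure balance, and pooling of sites is reserved for the blinded review. But pooling without a site term in the test changes nothing. A decision shortly before database lock also comes after both interim tests have been run.

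**Conclusion.** The mismatch is plain in the text, and its direction is not in doubt: if sites differ, the planned test is conservative and less efficient than an additive site-adjusted rank analysis. This is a question of efficiency, not validity, and the documents do not support a claim that the stated 80% power fails.

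The size rests entirely on an assumed between-site variance. With small sites pooled, the difference is about -2 to +3 points of power for a site SD up to 0.5. At SD 1.0, which is a large site effect (ICC about 0.23), it is about 5 to 8 points with 5 sites and 3 to 5 with 10, and the one-sided error of the planned test is about 1.4 to 1.8% instead of 2.5%. If sites do not differ, nothing is forgone. The change is worth making because it uses a factor the trial already balances and needs no further data.

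**What to change.** In SAP 14.5.1, and in the matching protocol text (synopsis, 9.1.1 and 11.4.2), specify that at each stage:

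1. The Day 7 score is ranked.
2. Treatment is tested with baseline score and site as additive terms (rank ANCOVA).
3. The one-sided p-value enters the inverse-normal combination.

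Do not cross site with baseline strata.

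Fix the site-pooling rule before the first interim, without reference to outcome or treatment arm. One option is to combine small sites into groups large enough for a site term to survive with 10 sites. A rule that pools every site under 6 patients per stage can leave no site term when recruitment is even. The grouped version was not itself simulated, so the sponsor should check its operating characteristics before adopting it.

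If the sponsor prefers to keep the baseline-only test as primary, state why site is omitted and pre-specify the site-adjusted rank analysis as a sensitivity analysis.

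Cost: a wording change in both documents (Protocol 2.8 requires IRB approval if the amendment is substantial), a pooling rule settled in advance, and up to about 2 points of power with pooling if sites do not differ. Without pooling, 10 sites cost about 3 to 5 points in that case.

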Hospitalized Severe disease	Non-invasive ventilation or high-flow oxygen	5																				
	Intubation, mechanical ventilation +/- additional organ support	6																				
Death	Death	7																				
Study Product / Intervention:	
RhC1INH will be administered (150 U/ml) at a 50 U/kg dose (max dose of 4200 U) as a slow intravenous injection in approximately 5 minutes every 12 hours for 4 days. A total of 8 doses will be administered. Both trial arms will receive SOC treatment according to local guidelines.
																					
Control Intervention (if applicable):	
Standard of care treatment including supplemental oxygen, antibiotics, off-label drugs for the treatment of COVID-19, and treatment for comorbid conditions and underlying disease.
																					

Number of Participants with Rationale:	
Approximately 120 subjects (80 in the active treatment arm, 40 in the SOC group).
 
The primary endpoint is a 7-point scale and the standard deviation σ can be expected as 1.5 points. A relevant effect δ is an advantage of at least 1 point. Then, the standardized difference is about $\delta/\sigma = 0.67$. For a fixed sample size design with a two-sided significance level of $\alpha = 0.05$ and a power of $1 - \beta = 0.80$, a sample size of $N = 2 \times 38$ is necessary. Because of a nonparametric test, we add 4 patients in each group, and because of drop-outs we add also 4 patients in each group to $N = 2 \times 46$. For a 2:1-randomization, a nonparametric analysis by the stratified Wilcoxon rank-test, and an adaptive group sequential analysis, the overall sample size is estimated as $120 = 80 + 40$.
 
All patients are hospitalized, and it is very unlikely that the primary endpoint at Day 7 will not be measured. Nevertheless, a drop-out rate of about 10% is included.
 
Two interim analyses after 32 and 80 patients are planned according to the Pocock adjusted levels $\alpha_P = 0.0221$. Based on the results of an interim analysis the sample size can be adjusted (Lehmacher, Wassmer, 1999). There are no prespecified futility margins, but the DSMB can stop the study in the case of insufficient interim results.

Study Duration:	Estimated 12 months
Principal Investigator(s):	[name].
Study Centre(s):	Multi-center

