2 DESIGN OF THE CLINICAL TRIAL

The study is a Phase IIa, randomized, open-label, multi-center, controlled (Standard of care/SOC), parallel group clinical trial of the efficacy and safety of a Ruconest® add-on treatment to SOC conducted in the United States.

It is planned to include a total of approximately 120 patients (80 in experimental and 40 in control group, allocation ratio 2:1).

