14.10 Interim Analysis

Two interim analyses after 40 and 80 patients are planned according to the Pocock adjusted levels $\alpha_p = 0.0221$. Based on the results of an interim analysis the sample size can be adjusted (Lehmacher, Wassmer, 1999). There are no prespecified futility margins, but the DSMB can recommend stopping the study in the case of insufficient interim results.

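### The SAP puts the first efficacy look at 40 patients and the current protocol puts it at 32; separately, the planned 95% intervals for the primary endpoint have no named effect measure and no sequential adjustment

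*SAP*

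**What the plan says.** **Look schedule.** SAP 14.5.1 has "Two adaptive interim analyses after 40 and 80 patients are planned according to the Pocock adjusted levels", and SAP 6 and 14.10 repeat 40 and 80 ("Two interim analyses after 40 and 80 patients are planned according to the Pocock adjusted levels"). Protocol 11.4.2 has "Two adaptive interim analyses after 32 and 80 patients are planned according to the Pocock adjusted levels". The protocol synopsis, 11.2 and 11.4.4 agree with it ("Two interim analyses after 32 and 80 patients are planned according to the Pocock adjusted levels"). Protocol 1.3 also sets the first DSMB safety review at 32 patients. Each document is consistent with itself.

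**Versions.** The protocol under review is Version 4.0 of 25 May 2021. SAP 1 and 3 cite Version 3.0 of 12 January 2021. SAP 1 adds that it covers amendments approved by the SAP's own date, which cannot be seen in the text available.

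**Sequential test.** The nominal level is 0.0221 in both documents. The planned total comes from SAP 2: "It is planned to include a total of approximately 120 patients". On combining stages, SAP 14.5.1 says "The results of the sequential groups are combined by the inverse-normal-method", and protocol 11.4.2 says the same. SAP 14.10 adds "Based on the results of an interim analysis the sample size can be adjusted". Neither document gives stage weights. SAP 14.8 ties 0.0221 to the interim analyses and does not mention the final one.

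**Intervals.** For the primary endpoint SAP 14.5.1 says "Furthermore, 95% confidence intervals will be determined", to be shown with box plots, and protocol 11.4.2 matches. No parameter is named. The only wording about intervals for treatment differences (SAP 14.5.2, protocol 11.4.3) concerns the qualitative secondary endpoints.

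**The concern.** The first efficacy look is a point at which the trial may stop or change its sample size, and it does so in an open-label study. Its timing should be the same in both governing documents before anyone sees comparative data. SAP 1 says the SAP is finalized after the blind review, which SAP 12 places just before the database is closed. That is too late to settle the timing of a look at 32 or 40 patients.

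The inverse-normal method protects alpha under a sample size change because its weights are fixed in advance, so the weights belong in the text.

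The interval question is separate and numerically larger. The stratified Wilcoxon test is judged at 0.0221, while an ordinary 95% interval corresponds to a test at 0.05. If ordinary intervals are reported, the clinical study report could show an interval that excludes no effect beside a primary test that failed. With no effect measure named, it is also unclear what the interval would be an interval for.

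**Working it through.** **Inputs from the documents.** Looks at 40/80 (SAP) or 32/80 (protocol), with the final analysis at 120; nominal level 0.0221; overall two-sided alpha 0.05; 2:1 allocation; SD 1.5 and effect 1 point, so the standardized effect is 1/1.5 = 0.67. **Assumptions.** Normal approximation, 120 evaluable patients, no sample size change.

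**1. Reproduce the plan's constant.** Seek c such that P(|Z1| > c or |Z2| > c or |Z3| > c) = 0.05 under no effect, where corr(Zi, Zj) = sqrt(ni/nj). For 40/80/120 the correlations are sqrt(40/80) = 0.707, sqrt(80/120) = 0.816 and sqrt(40/120) = 0.577. Numerical integration gives c = 2.2895, a nominal level of 0.02205, which rounds to the printed 0.0221. So the constant is the Pocock level for three equally spaced analyses, the final one included.

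**2. Alpha under each schedule.** The printed 0.0221 corresponds to z = 2.2886. Probability of first crossing at each look, under no effect:

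| Schedule and weights | Look 1 | Look 2 | Final | Total |
|---|---|---|---|---|
| 40/80/120 | 0.0221 | 0.0159 | 0.0121 | 0.0501 |
| 32/80/120, weights by stage size (32, 48, 40) | 0.0221 | 0.0173 | 0.0122 | 0.0516 |

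In the second row the level that restores 0.05 is 0.0214 (c = 2.3015).

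**3. Role of the weights.** The combined statistic is Zk = (w1 z1 + ... + wk zk) / sqrt(w1² + ... + wk²). Its null correlations depend only on the weights, not on the stage sizes. With equal weights, 32/80/120 therefore gives the first row again, 0.0501. If both weight sets stayed open and either could be used to reject, simulated alpha is about 0.053.

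**4. Ordinary intervals against the test.** With total n and 2:1 allocation, the information for the standardized effect is 1/(3/(2n) + 3/n) = 2n/9. The ordinary interval is estimate ± 1.960 SE and excludes no effect when |Z| > 1.960. The test needs |Z| > 2.2886. The two disagree at the final analysis when |Z| falls between those values. Simulation, 4,000,000 trials per case:

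| Standardized effect | Coverage at stopping, 40/80/120 | Coverage at stopping, 32/80/120 equal weights | Interval excludes no effect but final test not significant, 40/80/120 | Same, 32/80/120 equal weights |
|---|---|---|---|---|
| 0 | 92.8% | 92.7% | 2.2% | 2.3% |
| 0.3 | 93.9% | 93.5% | 8.7% | 9.2% |
| 0.5 | 94.7% | 94.4% | 9.1% | 9.9% |
| 0.67 | 95.0% | 94.8% | 4.3% | 4.7% |

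Check at zero effect, 40/80/120: 5.01% (test rejects) + 2.19% (interval alone excludes no effect) = 7.20%, so coverage is 92.8%. With size-based weights at 0.0221, coverage at zero effect is 92.6%.

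**5. Matched intervals.** Repeated intervals, estimate ± 2.289 SE, cover 95.0% at stopping under no effect and about 97.4-97.8% at effects of 0.3 to 0.67 (equal weights). Width ratio: 2.289/1.960 = 1.168.

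**The case against.** The best reply is that this is housekeeping. The SAP was written to Version 3.0, and other SAP text also looks older: SAP 4 has a four-week safety follow-up where protocol 4.4 has three months. The later-dated protocol says 32 throughout. The constant itself points to equal weights and to use at all three analyses, so the unstated weights and final level are missing detail. The documents never say the intervals are unadjusted, nor do they make them a decision rule, and at the planned effect there is almost no coverage loss. Equal weights and repeated intervals are one valid choice among several. All of this stands. It limits the weight of the point but does not remove it, because likely version lag explains two conflicting schedules without reconciling them.

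A reader might infer more in three ways, and the documents support none of them.

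- **That the mismatch breaks type I error control.** It does not: the schedule conflict moves alpha by at most about 0.16 percentage points (5.16% against 5%).
- **That the final test is run at a literal 5%, for an overall 7.2-7.4%.** SAP 14.5 refers to the 5% level unless otherwise stated. A Pocock design with 0.0221 is a statement otherwise, and 0.0221 is right only if the final analysis uses it too.
- **That look 1 requires a fixed difference in points.** The formula 2.2886 × 1.5 × sqrt(4.5/n) gives 1.15 points at n = 40 and 1.29 at n = 32, with stopping chances of 38% and 30% at the planned effect. Those figures describe a z-test with known SD. The planned stratified Wilcoxon test has no points threshold and would stop less often: roughly 31% at 40 patients and 24-25% at 32 in rank-test simulations under assumed score distributions.

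**Conclusion.** This should be fixed as a matter of alignment and clarification. The two current texts give different timings for the first efficacy look and must be reconciled before any look is taken; the consequence for alpha is 5.0% to about 5.16%. The larger numerical gap is in the intervals, and it is conditional. If they are ordinary 95% intervals, coverage at stopping falls to about 92.6-92.8% under no effect, with essentially no loss at the planned effect. They contradict a non-significant final test in about 2% of trials at zero effect, 9-10% at a standardized effect of 0.5 and 4-5% at 0.67.

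These figures rest on a normal approximation with no sample size change, not on the exact stratified rank test. Protocol 6.1 calls the trial exploratory. It nevertheless sets a 5% two-sided test with early stopping and tests the secondary endpoints only after primary success, so the rule has to be readable.

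**What to change.** 1. Put one look schedule in both documents and update the SAP's protocol reference to Version 4.0.
2. Before any interim look, state the inverse-normal weights and keep them after any sample size change. Equal weights, 1/sqrt(3) each, with two-sided 0.0221 at all three analyses hold under either schedule. Size-based weights at 32/80/120 are also valid but would need about 0.0214. Say that 5% is the overall alpha and that the chosen level applies at the final analysis.
3. Name the primary effect measure, for example the probability of a lower day-7 score under treatment (Mann-Whitney, ties counted half), stratified by baseline score.
4. Report intervals that match the sequential test. Repeated confidence intervals with a multiplier of about 2.289, built from the same weights, are one option; the per-look level is about 97.8% and overall coverage is 95%.

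**Cost.** No extra patients are needed. With 10% drop-out (72 + 36 = 108 evaluable), power at a standardized effect of 0.67 is about 85-86% under either schedule with equal weights (normal approximation). Intervals become about 17% wider and are conservative when there is a real effect. The stagewise stratified interval must be specified and programmed. Its agreement with the Wilcoxon test is only approximate, and least reliable at small stages: 32 patients at 2:1 means about 11 controls, split over baseline scores.
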